3.1.4 Study Enrollment

Patient enrollment will be facilitated using the Oncology Patient Enrollment Network (OPEN). OPEN is a web-based registration system available on a 24/7 basis. To access OPEN, the site user must have an active CTEP-IAM account (check at < <https://eapps-ctep.nci.nih.gov/iam/index.jsp> >) and a 'Registrar' role on either the lead protocol organization (LPO) or participating organization roster.

All site staff will use OPEN to enroll patients to this study. It is integrated with the CTSU Enterprise System for regulatory and roster data and, upon enrollment, initializes the patient position in the Rave database. OPEN can be accessed at <https://open.ctsu.org> or from the OPEN tab on the CTSU members' side of the website at <https://www.ctsu.org>.

Prior to accessing OPEN, site staff should verify the following:

- All eligibility criteria have been met within the protocol stated timeframes.
- All patients have signed an appropriate consent form and HIPAA authorization form (if applicable).

Note: The OPEN system will provide the site with a printable confirmation of registration and treatment information. Please print this confirmation for your records.

Further instructional information is provided on the CTSU members' web site OPEN tab or within the OPEN URL (<https://open.ctsu.org>). For any additional questions contact the CTSU Help Desk at [name] or [contact].

3.1.5 Timing

Patients must be enrolled before treatment begins. The date protocol therapy is projected to start must be no later than 7 business days after the date of study enrollment. **Patients who are started on protocol therapy prior to study enrollment will be considered ineligible and will not be able to receive further protocol therapy.**

See [Section 3.2](#) for timing requirements for eligibility studies and for timing requirements for baseline studies to be obtained prior to start of therapy. **Note: Repeat laboratory and imaging studies may be required if enrollment and start of therapy do not occur on the same day.**

Institutions are advised to plan ahead to ensure adequate and timely delivery of the investigational agent (see [Section 6.1](#) for details).

3.1.6 Institutional Pathology Report

Immediately following enrollment, the institutional pathology report for the diagnosis under which the patient is being enrolled must be uploaded into Rave. The report must include the associated study number and COG patient registration and accession numbers. Personal identifiers, including the patient's name and initials must be removed from the institutional pathology report prior to submission.

3.2 **Eligibility: Inclusion Criteria**

Important note: The inclusion criteria listed below are interpreted literally and cannot be waived. All clinical and laboratory data required for determining eligibility of a patient enrolled on this trial must be available in the patient's medical/research record. These source documents must be available for verification at the time of audit.

All clinical and laboratory studies to determine eligibility must be performed within 7 days prior to enrollment unless otherwise indicated. Laboratory values used to assess eligibility must be no older than seven (7) days at the start of therapy. Laboratory tests need not be repeated if therapy starts within seven (7) days of obtaining labs to assess eligibility. If a post-enrollment lab value is outside the limits of eligibility, or laboratory values are > 7 days old, then the following laboratory evaluations must be re-checked within 48 hours prior to initiating therapy: CBC with differential, bilirubin, ALT (SGPT) and serum creatinine. If the recheck is outside the limits of eligibility, the patient may not receive protocol therapy and will be considered off protocol therapy. Bone marrow aspirate (and biopsy, if applicable), must be obtained within 2 weeks prior to start of protocol therapy. If a bone marrow aspirate cannot be obtained, the patient is not eligible for enrollment.

3.2.1 Age: Patients must be \geq 1 month and $<$ 22 years of age at the time of study entry.

3.2.2 Diagnosis: Patients must have had histologic verification of juvenile myelomonocytic leukemia (JMML) at original diagnosis and currently have relapsed or refractory disease. The diagnosis is made based on the following criteria.

3.2.2.1 JMML Category 1 (all of the following):*

- Splenomegaly
- > 1000 ($1 \times 10^9/\mu\text{L}$) circulating monocytes
- $< 20\%$ Blasts in the bone marrow or peripheral blood
- Absence of the t(9;22) or BCR/ABL fusion gene

*The diagnostic criteria must include all features in category 1 and EITHER (i) one of the features in Category 2 OR (ii) two features from Category 3 to make the diagnosis.

3.2.2.2 JMML Category 2 (at least one of the following if at least two Category 3 criteria are not present):

- Somatic mutation in *RAS* or *PTPN11*
- Clinical diagnosis of NF1 or *NF1* gene mutation
- Homozygous mutation in *CBL*
- Monosomy 7

3.2.2.3 JMML Category 3 (at least two of the following if no Category 2 criteria are met):

- Circulating myeloid precursors
- White blood cell count, $> 10\,000$ ($10 \times 10^9/\mu\text{L}$)
- Increased Hemoglobin F for age
- Clonal cytogenetic abnormality
- GM-CSF hypersensitivity

3.2.3 Disease Status for Juvenile Myelomonocytic Leukemia (JMML) Patients:

3.2.3.1 Patients with refractory or relapsed JMML must have had at least one cycle of intensive frontline therapy or at least 2 cycles of a DNA demethylating agent with persistence of disease, defined by clinical symptoms or the presence of a clonal abnormality. Frontline therapy is defined as one cycle of intravenous chemotherapy that includes any of the following agents: fludarabine, cytarabine, or any anthracycline but specifically excludes oral 6-mercaptopurine. Frontline therapy will also include any conditioning regimen as part of a stem cell transplant. Patients who transform to AML at any point with more than 20% blasts are not eligible for this trial.

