1.3 Exploratory Aims

- 1.3.1 To describe the distribution of JMML diagnostic criteria in children with recurrent or refractory JMML.

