9.4 Evaluability for Response

Any patient who is enrolled and receives at least one dose of trametinib will be considered evaluable for response.

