APPENDIX III: RESPONSE CRITERIA FOR PATIENTS WITH JMML

Table 1: Variables for evaluation of response to therapy in JMML

Variables for Response	Definition of response			Definition of disease progression or relapse (applicable to all patients)	
	Assessment of CR and PR is feasible if the following are present before therapy	Requirement for CR for each variable (vCR)	Requirement for PR for each variable (vPR)	Requirement for PD for each variable (vPD)	
Clinical variables	1) WBC count	>20 × 10 ⁹ /L	3.0 – 15.0 × 10 ⁹ /L	Decreased by ≥50% over pretreatment but still >15 × 10 ⁹ /L	Increase by ≥50% and ≥20 × 10 ⁹ /L
	2) Myeloid and erythroid precursors and blasts in PB*	≥ 5%	0-1%	Decreased by ≥50% over pretreatment but still ≥ 2%	Increase from the baseline: < 5%: ≥ 50% increase and ≥ 5% ≥ 5%: ≥ 50% increase of total % of myeloid and erythroid precursors and blasts
	3) Platelet count	<100 × 10 ⁹ /L	>100 × 10 ⁹ /L	For patients starting with ≥ 20 × 10 ⁹ /L platelets: absolute increase of ≥ 30 × 10 ⁹ /L For patients starting with < 20 × 10 ⁹ /L platelets: increase by ≥ 100% and > 20 × 10 ⁹ /L	Development of transfusion dependency or if patients have the baseline of the platelet count of ≥30 × 10 ⁹ /L, decrease by ≥50% and <100 × 10 ⁹ /L
	4) BM blasts	≥5%	<5%	Decreased by ≥50% over pretreatment but still ≥5%	Increase from base line; < 5%: ≥ 50% increase and ≥ 5% ≥ 5%: ≥ 50% increase of BM blasts
	5) Spleen size				
	a) Clinical evaluation or	≥2 cm under the costal margin	No splenomegaly	50% decrease by cm under the costal margin	Increase by ≥100% if baseline <4cm from under the costa margin ≥50% if baseline 5-10cm >30% if baseline >10 cm
b) Sonography	Length of spleen ≥ 150% of upper limit of normal range	No splenomegaly	>25% decrease by length, but still splenomegaly	Increase by ≥25% of length	
6) Extramedullary disease#	Extramedullary leukemic infiltration	No evidence of extramedullary leukemic infiltration in any organ	-	Worsening or new lesions of extramedullary leukemic infiltration	
7) Cytogenetic response	Somatic cytogenetic abnormality detected	Normal karyotype	-	Reappearance or additional acquirement of cytogenetic abnormalities	
8) Molecular response	Somatic genetic anomalies detected**	Absence of somatic genetic anomalies	-	Reappearance or additional acquirement of JMML-specific somatic gene abnormalities	

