9) Chimerism response (only for patients after HSCT)	>15% autologous cells after allo-HSCT	Complete donor chimerism	-	50% increase and >5% increase of autologous cells and >5%	

CR: complete response, PR: partial response, PD: progressive disease, WBC: white blood cell, PB: peripheral blood, BM: bone marrow

*Myeloid precursors include promyelocytes, myelocytes, and metamyelocytes. The myeloid and erythroid precursors and blasts in PB are given as % of the total nucleated cells in PB (WBC including erythroblasts).

**in *NF-1*, *PTPN11*, *NRAS*, *KRAS*, *RRAS2*, or *CBL*, thus the mutation are thought to be initiating. In patients with germ-line *NF-1*, *PTPN11* or *CBL* mutation, only acquired mutations can be evaluated for response and relapse after therapy. The germ-line mutation remains even if patients achieved complete molecular response. The molecular response will be determined using the “JMML Mutant Allele Burden” assay.

Criteria for progression including WBC, platelet count and spleen size cannot be used in the setting of an active infection.

#Extramedullary disease includes infiltration of skin, lung, and very rarely cranial nerves or central nervous system.

Table 2: Definition of response following therapy other than HSCT in JMML

Clinical remission status: parameter 1-6 of table 1		Genetic remission status: parameter 7-9 of table 1	
Clinical complete remission (cCR)	Patient fulfills the criteria of CR of all applicable clinical variables 1-6 of table 1 The response parameters must be maintained for at least 4 weeks.	Genetic complete remission (gCR)	Defined if the patient shows a normal karyotype and absence of acquired mutations in PTPN11 , NF-1 , NRAS , KRAS , or CBL .
Clinical partial remission (cPR)	Defined if the patient does not fulfill the criteria of cCR, but vPR was achieved in at least one of clinical variables (1 – 6) and none of clinical variables showed vPD.	-	-
Clinical stable disease (cSD)	Defined if the patient does not fulfill the criteria of cCR and cPR, but none of the parameter showed vPD.	Genetic stable disease (gSD)	Defined if the patient does not fulfill the criteria of gCR, but none of the genetic parameters (7-9) showed vPD.
Clinical progressive disease (cPD)	Defined if any of the parameters 1-6 showed vPD.	Genetic progressive disease (gPD)	Defined if any of the parameters 7-9 showed vPD.

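### Clinical CR has no minimum number of assessable variables, so an unchanged patient admitted on a clonal abnormality alone can be scored either PR or SD on the primary endpoint

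*Combined protocol and SAP*

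**What the plan says.** **Entry.** Section 3.2.3.1 requires prior therapy with "persistence of disease, defined by clinical symptoms or the presence of a clonal abnormality". The *or* makes a clonal abnormality sufficient. Section 3.2.2 asks for histologic verification of JMML "at original diagnosis and currently have relapsed or refractory disease", so the splenomegaly and monocyte criteria describe the original diagnosis. Section 1.3 has an exploratory aim, "To describe the distribution of JMML diagnostic criteria in children with recurrent or refractory JMML", which suggests these features are not assumed to be present at entry.

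**Assessability.** Appendix III Table 1 heads its baseline column "Assessment of CR and PR is feasible if the following are present before therapy". For the clinical variables the thresholds are WBC above 20 × 10⁹/L, peripheral precursors and blasts at least 5%, platelets below 100 × 10⁹/L, marrow blasts at least 5%, spleen at least 2 cm (or at least 150% of the upper limit by sonography), and extramedullary infiltration.

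**Clinical and genetic categories.** Table 2 defines cCR as "Patient fulfills the criteria of CR of all applicable clinical variables 1-6 of table 1" and adds "The response parameters must be maintained for at least 4 weeks". By contrast, cPR needs a partial response in at least one clinical variable. cSD is what remains when neither cCR nor cPR is met and nothing has progressed. Genetic stable disease is "Defined if the patient does not fulfill the criteria of gCR, but none of the genetic parameters (7-9) showed vPD".

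**Overall response.** Section 10.2 maps cCR with gSD to PR, cSD with gSD to SD, and gCR with cSD to CR. Section 9.3 counts PR or CR before progression as a response. Section 9.4 states: "Any patient who is enrolled and receives at least one dose of trametinib will be considered evaluable for response".

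**The concern.** The primary aim is the objective response rate. The trial stops for futility only on 0 responses in 10 and is positive on 3 in 20, so each classification carries weight. The response rules do not say what to do with a patient who has no clinical variable past its Table 1 threshold. Read one way, that patient reaches clinical CR by satisfying an empty list and becomes an overall PR while nothing has improved. Read the other way, the patient has stable disease and can respond only by clearing the clone. The trial is open-label and single-arm, and nothing in the plan settles the choice before outcomes are known.

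The protocol leaves room for such patients. Transplant conditioning counts as frontline therapy, and enrolment is allowed from 3 months after a transplant without TBI. One cycle of intensive chemotherapy, or two of a demethylating agent, with a residual clone is enough. Hydroxyurea may continue until 24 hours before treatment, so a baseline WBC below 20 × 10⁹/L is possible.

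**Working it through.** **1. Tracing two hypothetical patients through the rules**

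- *Patient A*: persistent *PTPN11* mutation, WBC 14, peripheral precursors 1%, platelets 130, marrow blasts 3%, no splenomegaly, no extramedullary disease. Disease status under 3.2.3.1 is met by the clone. No Table 1 clinical threshold is met, and every clinical variable already has its CR value at baseline.
- *Patient B*: the same, but precursors 3% and spleen 1 cm. Still below every threshold. If *applicable* means past the baseline threshold, no variable applies. If it means merely measurable, B fails CR on precursors (0–1% required), and probably on spleen.

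For A, cCR is satisfied on either meaning of *applicable*, provided the values hold for 4 weeks. Only the Table 1 heading, taken to mean that CR cannot be assessed at all, makes A cSD. With an unchanged clone (gSD), Section 10.2 gives PR on the first route and SD on the second.

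**2. Reproducing the plan's figures**

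Inputs from Section 9.2: stage 1 of 10, stop on 0; stage 2 of 10 more, effective on 3 or more of 20; rates 5% and 25%.

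P(effective) = Σ over x ≥ 1 of Bin(x; 10, p) × P(Bin(10, p) ≥ max(0, 3 − x)).

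This gives 0.0686 at 5% and 0.8820 at 25%, with early stopping 0.5987 and expected size 14.01 at 5%. These agree with the stated 0.069, 0.882, 59.9% and 14.01.

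**3. Adding k patients scored PR for not progressing**

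Assumptions: k of the 20 are such patients, split at random (hypergeometrically) between the stages; the others respond at 5%; all k avoid progression long enough.

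- k = 1. In stage 1 (probability 0.5), the futility stop cannot occur and 2 or more of the other 19 are needed: 1 − 0.95¹⁹ − 19(0.05)(0.95¹⁸) = 0.2453. In stage 2 (probability 0.5): 0.2027. The average is 0.224.
- k = 2. None in stage 1 (45/190 = 0.2368): a positive result needs only one stage 1 response, 1 − 0.95¹⁰ = 0.4013. Otherwise: 1 − 0.95¹⁸ = 0.6028. Total 0.2368 × 0.4013 + 0.7632 × 0.6028 = 0.555.
- k = 3. None in stage 1 (120/1140 = 0.1053): 0.4013. Otherwise 1. Total 0.1053 × 0.4013 + 0.8947 = 0.937.

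**4. Relaxing the last assumption, and the opposite reading**

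The middle column gives each of the k patients a 50% chance of avoiding progression long enough and counts the rest as non-responders. The 50% is an assumption. The last column treats all k as unable to respond, with 25% in the others.

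| k of 20 | P(effective) at 5%, all avoid progression | P(effective) at 5%, half avoid it | Power at 25%, k cannot respond |
|---|---|---|---|
| 0 | 0.069 | 0.069 | 0.882 |
| 1 | 0.224 | 0.142 | 0.860 |
| 2 | 0.555 | 0.255 | 0.833 |
| 3 | 0.937 | 0.394 | 0.803 |

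**The case against.** A reader might infer that these patients definitely score PR. The documents do not support that. The Table 1 heading speaks of assessment being feasible only when the abnormality is present, and cSD is available for a patient in whom CR cannot be shown. Because *applicable* is undefined, patient B in particular may not reach cCR. This part of the objection stands: the defect is that the rule is unspecified, not that it plainly yields PR.

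Nor is the PR automatic. The progression column applies to every patient. Precursors rising from 3% to 5%, a spleen from 1 to 2 cm, WBC from 14 to 21, or a new JMML mutation would each give PD. The first results column is therefore an upper bound for each k.

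The number of such patients has no source. Section 2.1 describes JMML with massive splenomegaly and thrombocytopenia, and k may be zero. Section 10.2 attributes the criteria to an international consensus panel, and how that source handles the case cannot be seen here.

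Could Category 1 be required at entry? That would usually make the spleen assessable, but the wording points to original diagnosis. Even then, Category 1 gives no spleen size, so a 1 cm spleen could pass entry and miss the 2 cm threshold.

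It is also tempting to call these patients near-certain non-responders on the stable-disease reading, because Section 2.2.1 reports that mutant cells persisted under MEK inhibition. Those are mouse data, and Section 10.2 gives patients a genetic route to CR.

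**Conclusion.** The gap is real. Eligibility, Appendix III and Sections 9.3, 9.4 and 10.2 together allow a patient with no improvement to be scored as a responder, and no passage says whether that is intended. The plan's 0.069 and 0.882 are arithmetically correct; the weakness lies in the endpoint definition that feeds them. It would be wrong to say that the trial's type I error is 0.937, or any other figure in the table. Those are scenarios resting on an assumed k, on the literal reading of cCR, and on an assumed chance of avoiding progression. What can be said is that one such patient among 20 would raise the false-positive probability from 0.069 to between 0.142 (half avoid progression) and 0.224 (all do), and that one scored PR in stage 1 removes the futility stop. This should be fixed; confidence is moderate because the reading is disputed and k is unknown.

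**What to change.** In Appendix III Table 2, state that cCR and cPR require at least one of clinical variables 1–6 to have met its Table 1 baseline threshold. A patient with none is at best cSD on the clinical axis and can respond only through gCR. Leave eligibility and the Section 9.4 denominator as they are. In Section 9.3, add a supporting response rate among patients with at least one assessable clinical variable at baseline.

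This takes one rule and one analysis on data already collected. It closes the false-positive route: with k such patients in the denominator, P(effective) at 5% stays at or below 0.069, provided they reach gCR no more often than 5%. The cost is a reported response rate that may be lower and, if such patients do not reach gCR, power at 25% of 0.860, 0.833 or 0.803 for k = 1, 2 or 3 instead of 0.882. The supporting analysis shows how far the primary rate is diluted but does not restore that power.

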3.2.3.2 Performance Level

Patients must have a Lansky or Karnofsky performance status score of ≥ 50 , corresponding to ECOG categories 0, 1 or 2. Use Karnofsky for patients > 16 years of age and Lansky for patients ≤ 16 years of age. Patients who are unable to walk because of paralysis, but who are up in a wheelchair, will be considered ambulatory for the purpose of assessing the performance score.

(See https://members.childrensoncologygroup.org/prot/reference_materials.asp)

3.2.4 Prior Therapy

Patients must have fully recovered from the acute toxic effects of all prior chemotherapy, immunotherapy, or radiotherapy prior to study enrollment.

- a. Myelosuppressive chemotherapy: Patients must have completely recovered from all acute toxic effects of chemotherapy, immunotherapy or radiotherapy prior to study enrollment. At least 14 days must have elapsed since the completion of cytotoxic therapy, with the exception of hydroxyurea.
- Note:** Cytoreduction with hydroxyurea can be initiated and continued for up to 24 hours prior to the start of protocol therapy.
- b. Hematopoietic growth factors: At least 14 days after the last dose of a long-acting growth factor (e.g., pegfilgrastim) or 7 days for short-acting growth factor. For agents that have known adverse events occurring beyond 7 days after administration, this period must be extended beyond the time during which adverse events are known to occur.
- c. Biologic (anti-neoplastic agent): At least 7 days must have elapsed since completion of therapy with a biologic agent. For agents that have known adverse events occurring beyond 7 days after administration, this period prior to enrollment must be extended beyond the time during which adverse events are known to occur.
- d. Monoclonal antibodies:
- i. At least 30 days after the completion of any type of immunotherapy, e.g. tumor vaccines.
 - ii. At least 3 half-lives must have elapsed since prior therapy that included a monoclonal antibody. (See posting of half-lives for commonly used monoclonal antibodies on the DVL homepage (<https://members.childrensoncologygroup.org/Disc/devtherapeutics/default.asp>)).
- e. Radiotherapy:
- i. ≥ 2 weeks must have elapsed since local palliative XRT (small port)
 - ii. ≥ 6 months must have elapsed if prior craniospinal XRT was received, if $\geq 50\%$ of the pelvis was irradiated, or if TBI was received
 - iii. ≥ 4 weeks must have elapsed if other substantial bone marrow irradiation was given.
- f. Stem Cell Transplant or Rescue without TBI: No evidence of active graft vs. host disease and ≥ 3 months must have elapsed since transplant. ≥ 4 weeks must have elapsed since any donor lymphocyte infusion.

3.2.5 Organ Function Requirements

3.2.5.1 Adequate Bone Marrow Function Defined As:

- Patients must not be known to be refractory to red blood cell or platelet transfusions.

3.2.5.2 Adequate Renal Function Defined As:

- Creatinine clearance **or** radioisotope GFR ≥ 70 mL/min/1.73 m² **or** a serum creatinine based on age/gender as follows:

Age	Maximum Serum Creatinine (mg/dL)	
	Male	Female
1 month to < 6 months	0.4	0.4
6 months to < 1 year	0.5	0.5
1 to < 2 years	0.6	0.6
2 to < 6 years	0.8	0.8
6 to < 10 years	1	1
10 to < 13 years	1.2	1.2
13 to < 16 years	1.5	1.4
≥ 16 years	1.7	1.4

The threshold creatinine values in this Table were derived from the Schwartz formula for estimating GFR utilizing child length and stature data published by the CDC. [38](#)

3.2.5.3 Adequate Liver Function Defined As:

- Total bilirubin ≤ 1.5 x upper limit of normal (ULN) for age
- SGPT (ALT) ≤ 3 x ULN (135 U/L (for the purpose of this study, the ULN for SGPT is 45 U/L)
- Serum albumin ≥ 2 g/dL.

3.2.5.4 Adequate Cardiac Function Defined As:

- Shortening fraction of $\geq 27\%$ by echocardiogram OR Ejection fraction of $\geq 50\%$ by MUGA
- Corrected QT (QTcB) interval <450 msec

3.2.6 Patients must be able to swallow tablets or liquid; use of a nasogastric or G tube is also allowed.

